6.1.3. Analysis Sets

=

The **Full analysis set** consists of all enrolled subjects who sign informed consent. The full analysis set will be used for AE reporting in general and ancillary objective [REDACTED]

The **Modified Intention-to-Treat (mITT)** cohort is the subset of subjects who maintain informed consent at least until the index cryoablation procedure was finished. For endpoints analyzed in this group of subjects, the standard Intention-to-Treat (ITT) protocol applies immediately upon insertion of the cryoballoon catheter into the subject's vasculature. The mITT cohort will be used in the analysis of the primary efficacy objective, the secondary objective regarding Quality of Life (QoL), and the ancillary objective [REDACTED]. The mITT dataset will be used in the analysis of the primary efficacy and safety objectives, as well as for the secondary objective and ancillary objectives [REDACTED].

This study has planned submissions to the US FDA and Japan PMDA. The Pre-Market Approval Submission (PMA-S) to the US FDA will include subjects from centers in US and Canada. If full 12-month data is available from Japan subjects at the time of PMA-S submission, the Japan data may be included in the PMA-S submission. The submission to the Japan PMDA will include analysis from data collected from all four geographies. The analyses for both submissions will follow the same pre-specified analysis procedures, so this SAP will not distinguish between the PMDA submission cohort (165 subjects expected) vs. the subset of subjects used for the PMA-S (150 subjects expected) except when differences due to sample size are relevant to the discussion.

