
Sample Size and Analysis Timing
	
Up to 225 subjects will be enrolled world-wide. In the US, Canada and Europe, up to 200 subjects will be enrolled to ensure 150 subjects are treated with an Arctic Front Advance Cardiac CryoAblation Catheter. The maximum number of subjects treated at Canadian and European centers combined is 45 subjects.
 
Up to 25 subjects will be enrolled in Japan to ensure 15 subjects are treated with an Arctic Front Advance Cardiac CryoAblation Catheter.
 
At the completion, the last 12 month visit from the 150 enrolled and treated subjects from the US, Canada and Europe, a PMA-S will be submitted to the FDA. Study data from the Japanese centers will not be included in the PMA-S submission but will be made available.
 
A final report will be submitted to Japan PMDA at the completion of the last 12 month visit from the 15 treated Japanese subjects. Study data from all 165 treated subjects will be included in this report.

Inclusion/Exclusion Criteria
	
Inclusion Criteria
 
 • Documentation of symptomatic persistent AF 
 ○ Defined as having a continuous episode lasting longer than 7 days but less than 6 months documented by consecutive ECG recordings OR ○ Defined as having a continuous episode lasting longer than 7 days but less than 6 months documented by an ECG recording and one doctor note indicating patient had symptoms consistent with AF • Failure or intolerance of at least one Class I or III antiarrhythmic drug • Age 18 or older (or older than 18 if required by local law) 
Exclusion Criteria
 
 • Left atrial diameter > 5.0 cm (anteroposterior) • Prior left atrial ablation or surgical procedure (including left atrial appendage closures) • Presence or likely implant of a permanent pacemaker, biventricular pacemaker, loop recorder, or any type of implantable cardiac defibrillator (with or without biventricular pacing function) within 12 months • Presence of any pulmonary vein stents • Presence of any pre-existing pulmonary vein stenosis • Pre-existing hemidiaphragmatic paralysis • Presence of any cardiac valve prosthesis

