11.2. Subject Enrollment

Patients will be screened to ensure they meet all of the inclusion and none of the exclusion criteria prior to study enrollment. IRB/MEC and Medtronic approval of this CIP and the Patient Informed Consent Form must be obtained prior to enrolling subjects in the study. Enrollment of the subject must occur prior to performing any study procedures. Subjects are enrolled at the time the Patient Informed Consent Form is signed and dated.

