13.19. Subject Withdrawal or Discontinuation

A subject can withdraw from the study or the [REDACTED] sub-study at any time. If the subject wishes to exit from the study (i.e. the subject revokes consent), the center is required to document the reason for exit on an eCRF. In addition, centers shall follow the regulations set forth by their IRB/MEC. It is recommended to follow the subject until all ongoing device and/or procedure-related adverse events are resolved or unresolved with no further actions planned. For countries following ISO, permission may be requested to follow-up with the subject outside of the study due to withdrawal based on problems related to the study device safety or performance. Following exit, subjects will continue to receive standard medical care. All data available through the time of the subject's exit will be used for analysis.

Reasons for study exit include:

- Subject lost to follow-up
- Subject did not meet inclusion/exclusion criteria after consent and did not undergo an ablation procedure
- An Arctic Front Advance catheter was not used during the subject's ablation procedure
- Subject did not provide consent or data use protection authorization
- Subject chooses to withdraw (e.g., consent withdrawal, relocation to another geographic location)
- Investigator deems withdrawal necessary (e.g., medically justified, inclusion/exclusion criteria not met, failure of subject to maintain adequate study compliance)
- The sponsor decides the study will be closed or a particular center will be closed

The following information is required to be collected at study exit:

- Reason for exit must be documented on the eCRF and in the subject's medical record

In the case that the subject is determined to be lost to follow-up, details of a minimum of two attempts and the method of attempt (e.g., one letter and one phone record or two letters) to contact the subject must be recorded.

An unscheduled office visit should be attempted if the subject exits the study outside of a scheduled follow-up visit.

14. Risks and Benefits

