4.4. Ancillary Objectives

- [REDACTED]

[figure not shown]
5. Investigation Plan

The purpose of the study is to provide data demonstrating the safety and effectiveness of the Arctic Front Advance and Freezor MAX Cardiac CryoAblation Catheters for the treatment of symptomatic drug refractory persistent AF. The study is proposed by the sponsor as a result of feedback received from the US Food and Drug Administration (FDA) on pre-submission Q151184, regarding a proposal to expand the indications for use for the Arctic Front Advance to include patients with persistent AF. The study is also designed to expand the indication for the Freezor MAX Cardiac CryoAblation Catheter. The proposed indication for the Arctic Front Advance CryoAblation Catheter is as follows: The Arctic Front Advance Cardiac CryoAblation Catheters are indicated for the treatment of drug refractory recurrent symptomatic paroxysmal and persistent atrial fibrillation. The proposed indication for the Freezor MAX Cardiac CryoAblation Catheter is as follows: The Freezor MAX Cardiac CryoAblation Catheters are indicated for use as an adjunctive device in the endocardial treatment of paroxysmal and persistent atrial fibrillation in conjunction with the Arctic Front Advance Cardiac CryoAblation Catheter for the following uses: gap cryoablation to complete electrical isolation of the pulmonary veins, cryoablation of focal trigger sites and creation of ablation line between the inferior vena cava and the tricuspid valve. A sub-study [REDACTED]

[REDACTED]

Medtronic, Inc. is sponsoring the STOP Persistent AF Study; a prospective, interventional, multi-center, non-randomized, single arm, unblinded clinical study. [REDACTED]

[REDACTED] Up to 225 subjects will be enrolled world-wide. In the US, and Canada, up to 200 subjects will be enrolled to ensure 150 subjects are treated with an Arctic Front Advance Cardiac CryoAblation Catheter. The maximum number of subjects treated at Canadian centers combined is 45 subjects. Up to 25 subjects will be enrolled in Japan to ensure 15 subjects are treated with an Arctic Front Advance Cardiac CryoAblation Catheter. The maximum number of subjects treated at Japanese centers is 15 subjects.

6. Statistical Methods

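### SAP 6.1.3 names all consented subjects as the set for general AE reporting, so descriptive procedure- and system-related AE rates, read as written, are understated by up to 25.0% (PMA-S) or 26.7% (PMDA) at the enrolment caps

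*SAP*

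**What the plan says.** SAP 6.1.3 defines the full analysis set as one that "consists of all enrolled subjects who sign informed consent", and adds: "The full analysis set will be used for AE reporting in general and ancillary objective" (the ancillary objective is redacted). Treatment is not a condition of membership. Protocol 11.2 fixes the moment of entry: "Subjects are enrolled at the time the Patient Informed Consent Form is signed and dated".

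Both documents plan for more consented than treated subjects. SAP section 5 says of the North American centres that "up to 200 subjects will be enrolled to ensure 150 subjects are treated with an Arctic Front Advance Cardiac CryoAblation Catheter", of Japan that "Up to 25 subjects will be enrolled in Japan to ensure 15 subjects are treated with an Arctic Front Advance Cardiac CryoAblation Catheter", and, for the total, "Up to 225 subjects will be enrolled world-wide". The protocol synopsis gives the treated total for the PMDA report: "Study data from all 165 treated subjects will be included in this report".

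Protocol 13.19 lists how a consented subject can leave untreated, including "Subject did not meet inclusion/exclusion criteria after consent and did not undergo an ablation procedure" and a procedure in which the study balloon catheter was not used. Protocol 13.4 adds exit when a left atrial thrombus is seen.

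The primary safety objective is handled differently. SAP 6.2.3.3 analyses it in the mITT set, meaning subjects in whom the balloon catheter entered the vasculature. Protocol 15.2 starts AE collection at consent and covers procedure-related, system-related, cardiovascular and serious events.

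**The concern.** A subject who exits before any procedure cannot have an event caused by the procedure or the cryoablation system. Counting that subject in the denominator of a related-AE rate lowers the rate without adding information, and always in the favourable direction.

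The primary composite is narrow, so much of the procedural safety picture lies outside it: groin haematoma, pseudoaneurysm, arteriovenous fistula, gastroparesis, phrenic nerve injury that resolves by 12 months, and bleeding without transfusion. In a single-arm, unblinded study these rates have no concurrent control and will be read against outside figures. Protocol Appendix G invites that comparison: it tabulates literature complication rates (Table 24) as an aid to judging whether events are unexpected. SAP section 3 says the SAP governs the PMA submission, the final report and planned publications, so the denominator would carry into all of them.

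**Working it through.** **1. The plan's own safety figure, reproduced.** The documents give no AE rate on the full analysis set. The nearest stated figure is the power for primary safety in SAP 7.2 (exact binomial, 5% against 13%, one-sided 0.025).

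- PMA-S: 150 × 0.9 = 135 subjects, objective met with 9 or fewer events. P(X ≤ 9 | 135, 0.13) = 0.0141 and P(X ≤ 9 | 135, 0.05) = 0.860.
- PMDA: 165 × 0.9 = 148.5, taken as 148, objective met with 11 or fewer events. Alpha is 0.0233 and power 0.932.

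All four values match the SAP. The calculation starts from treated numbers, so the question here does not touch it.

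**2. Inputs for the dilution.**

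- PMA-S: at most 200 enrolled, 150 treated (SAP section 5).
- PMDA: at most 225 enrolled (SAP section 5), 165 treated (protocol synopsis).

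**3. Formula.** Let x be the number of subjects with a related AE, E the exposed subjects (index procedure started) and N the consented subjects. The rate among the exposed is x/E. The rate on the full analysis set is x/N = (x/E) × (E/N). The relative understatement is therefore 1 - E/N, whatever the event. The same factor applies to any AE defined as starting on or after the index procedure.

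**4. Results, taking E as the treated number.** The 5% is the plan's assumed primary safety rate, borrowed only as an example of a rate among the exposed.

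| Cohort | Enrolled | Exposed | Relative understatement | 5% would show as |
|---|---|---|---|---|
| PMA-S | 160 | 150 | 6.3% | 4.69% |
| PMA-S | 170 | 150 | 11.8% | 4.41% |
| PMA-S | 180 | 150 | 16.7% | 4.17% |
| PMA-S | 190 | 150 | 21.1% | 3.95% |
| PMA-S (cap) | 200 | 150 | 25.0% | 3.75% |
| PMDA | 195 | 165 | 15.4% | 4.23% |
| PMDA (cap) | 225 | 165 | 26.7% | 3.67% |

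**5. Effect of attempted procedures.** If some subjects outside the treated count had a procedure started without balloon insertion, E rises and the understatement falls. Assuming 5 such subjects among 200 enrolled, for illustration, it is 1 - 155/200 = 22.5%.

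**The case against.** Four points can be made for the plan as it stands.

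*A consent-based set has a proper safety purpose.* AE collection starts at consent, so only this set captures every collected event. A reader might also infer that anyone outside the treated set cannot have a related event. The documents do not support that. Protocol Table 9 ties procedure-relatedness to any part of the procedure and includes the sheath and mapping catheter in the system. Protocol 13.19 and SAP 6.1.1 foresee subjects taken to a procedure in whom the study balloon was not used. Access or sheath complications in such subjects fall outside mITT but inside the full set. This point stands, and it is why the remedy should not simply substitute mITT.

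*Naming a reporting set is not a rate formula.* The SAP prints no AE incidence formula or table shell, and other passages describe the reports in terms of treated subjects. That is fair: the understatement follows from the rule as written, and the sponsor may have intended something else. But the only visible assignment for AE reporting is the full set, and an analyst who followed it would divide by it.

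*Some text cannot be seen.* The ancillary objectives are redacted, some are assigned to mITT, and the available SAP runs from 6.5 directly into subgroup material. A reader might infer that primary safety is the only result placed on treated subjects. That cannot be established, and primary efficacy and quality of life are also assigned to mITT.

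*The caps are maxima and no test is affected.* Both are true. The documents give no expected proportion of untreated subjects, and general AE reporting is descriptive.

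**Conclusion.** The point holds for descriptive rates of procedure- and system-related AEs outside the primary composite. It rests on three conditions: that SAP 6.1.3 is applied as written, that no unseen text sets another denominator, and that some consented subjects exit before any procedure. The 25.0% and 26.7% are ceilings reached only if enrolment runs to its caps with treated numbers at target. The actual figure depends on enrolment that the plan does not predict.

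Two larger conclusions that a reader might draw are not supported. The primary safety conclusion is not biased by this, because its analysis against 13% is on the mITT set. Nor is every AE incidence understated by the same factor: pre-procedure events and unrelated events can occur in untreated subjects, for whom the full set is a legitimate population. What remains is an avoidable bias in the favourable direction, in figures that a single-arm study asks its readers to compare with outside rates. It should be corrected.

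**What to change.** Amend SAP 6.1.3 to separate listing from rates:

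- Rates of procedure-related and system-related AEs, and of AEs starting on or after the index procedure, use as denominator all subjects in whom the index procedure was started. This includes those whose procedure was attempted without balloon insertion, so that access and sheath events are kept.
- The full analysis set is kept for listing all AEs from consent, including those before the procedure.
- AE tables print the number enrolled and the number with a procedure started, so a reader can convert between the two.

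If redacted text already sets such a denominator for some summaries, 6.1.3 should refer to it. The change costs a sentence or two and a table denominator. It needs no new data and leaves the primary tests and their power as they are. The drawback is that the reported AE rates become slightly less favourable.

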	2AF284	Japan (investigational)																											
	2AF233	Canada (non-investigational)	Medtronic, Inc.																										
	2AF283	Europe (non-investigational)																											
Freezor MAX Cardiac CryoAblation Catheter	239F3	US (investigational)	Medtronic, Inc.																										
	239F5	Japan (investigational)																											
	209F3	Canada (non-investigational)	Medtronic, Inc.																										
	209F5	Europe (non-investigational)																											
Primary Objectives	
 • Demonstrate an acceptable efficacy success rate at 12 months after the pulmonary vein isolation (PVI) ablation procedure. • Demonstrate an acceptable safety profile of the pulmonary vein isolation (PVI) ablation procedure. 																												
Secondary Objective	
 1. Demonstrate an improvement in quality of life between baseline and 12 months as measured by the Atrial Fibrillation Effect on QualiTY-of-life Questionnaire (AFEQT) and Medical Outcome Study Short Form-12 (SF-12) questionnaires 																												
Ancillary Objectives	
 ■ [REDACTED] 																												
Study Design	
The study is prospective, interventional, multi-center, non-randomized, single arm, unblinded clinical study. The study will be conducted at up to 25 centers located in the US, Canada, Europe and Japan. The study objectives will be analyzed for a Premarket Approval Supplement (PMA-S) after all subjects from the US, Canada and Europe complete 12 months of follow-up after the index ablation procedure.
																												

Medtronic Confidential

	
Study data from the Japanese centers will not be included in the PMA-S submission, but will be included in a submission to Japan Pharmaceuticals and Medical Device Agency (PMDA).
 
The Japanese subjects are required by PMDA to support an expanded indication to the persistent AF population in Japan. The PMDA cohort will be analyzed separate to the PMA-S because participation and enrollment in Japan is anticipated to start later than the rest of the PMA-S cohort.

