7.1. Duration

Subjects from all geographies will be followed for 12 months after the index cryoballoon ablation procedure and then be exited from the study. Accordingly, the expected total study duration is approximately 2 years and 2 months, representing 14 months of enrollment and 12 months of subject follow-up. Subjects will not be replaced with newly enrolled subjects upon early study exit. The objectives will be analyzed for a Premarket Approval Supplement (PMA-S) after all subjects from the US, Canada and Europe complete 12 months of follow-up after the index ablation procedure. Study data from the Japanese centers will not be included in the PMA-S submission. A final report will be submitted to Japan PMDA at the completion of the study.

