17.1. General Considerations

Two analysis cohorts have been defined for this study:

- PMA-S cohort (US/Canada/Europe cohort) – subjects from US, Canada, and Europe centers
- PMDA cohort (US/Canada/Europe/Japan cohort) – subjects from US, Canada, Europe, and Japan centers

Analysis methods are detailed for all objectives in sections 17.1- 17.5. The same methods will be used for both the PMA-S cohort, and also the PMDA cohort. The estimated sample sizes are 150 subjects for the PMA-S cohort, and 165 subjects for the PMDA cohort. The PMDA cohort will have a slight increase in statistical power given 165 subjects will be utilized versus 150.

The Statistical Analysis Plan (SAP) will be created prior to data analysis and include a comprehensive description of the statistical methods to be included in study reports. Any change to the data analysis methods described in the CIP will require an amendment only if it changes a principal feature of the CIP. Any other change to the data analysis methods described in the CIP, and the justification for making the change, will be described in the clinical study report. Medtronic employees or their designated representatives will perform all statistical analyses.

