Evidence for this study will be used in submissions to two separate regulatory bodies. The submission for indication change to the Japan Pharmaceuticals and Medical Devices Agency (PMDA) will include analysis based on subjects from all available geographies (US, Canada, and Japan), and is referred to as the PMDA cohort in this document. Meanwhile, the Pre-Market Approval Supplement (PMA-S) to the US Food and Drug Administration (FDA) will include data from subjects treated in the US, and Canada; these subjects are referred to as the "PMA-S" cohort in this SAP. For both PMA-S and PMDA cohorts, it will be assessed whether site-to-site and geographical heterogeneity exists in the rate of pre-specified primary endpoints using a random-effects meta-analytic approach. The R statistical software platform will be used to evaluate whether sites exhibit significant heterogeneity in event rates, and whether geography (a three-level categorical variable representing whether a site is located in the US, Canada, or Japan) moderates any statistically significant heterogeneity that is observed. Models will be fit separately for each primary outcome. Testing will not be performed for outcomes or strata in which heterogeneity cannot be assessed in a meaningful way (for example, if < 5 events are observed in all subjects). If a Cochran's Q-test for heterogeneity shows $p < 0.05$, it will be taken as evidence of significant heterogeneity between sites. Evidence of between-site heterogeneity will not preclude pooling data; rather, it will prompt further investigation into the sources of the apparent differences in event rates between sites. At a minimum, findings of analyses on heterogeneity between study sites and between all US, Canadian and Japanese study centers will be shown in the final report in a table by endpoint. Heterogeneity analysis findings will not change the composition of the PMA-S and PMDA cohorts as defined above. Analysis of heterogeneity will be performed within the mITT dataset, like the primary safety and efficacy analyses are.

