7.2. Sample Size Determination for Safety Endpoint

Sample size for the primary safety objective was estimated using Proc Power in SAS 9.4. Parameters for the safety endpoint power calculation were a one-sided exact binomial test with $\alpha = 0.025$ to declare a significant difference between a performance goal (PG) of 13% when the true safety event rate was 5.0% and the sample size was 135 – 148 subjects analyzed. The following code for proc power can be used to replicate the sample size calculation under these conditions.

[figure not shown]
Computed Power

	N Total	Lower Crit	Actual Alpha	Power
(PMA-S)	135	9	0.0141	0.860
(PMDA)	148	11	0.0233	0.932

This calculation shows that with 10% attrition between enrollment and 12-month follow-up visits, 150 subjects in the US and Canada will provide 86% power to accept the alternative hypothesis for a rate of 5%. The power for the PMDA dataset, with an estimated 15 extra subjects (for 165 total), will be 93% for the primary safety objective.

Power for both endpoints by sample size (accounting for attrition, and assuming the constraints mentioned above) is shown below in figure 2:

**Figure 2:
Power vs. Enrollment for STOP Persistent AF Primary Endpoints**

8. Validation Requirements

Verification of analyses of both the primary efficacy objective and the primary safety objective will be completed with level I validation (independent programming). Secondary and ancillary objectives will be validated with a minimum of level II validation. Analyses that are not related to primary objectives or ancillary endpoints will be validated at a minimum of level II validation if being presented externally in an abstract or publication.

9. References

Hommel, G. A stagewise rejective multiple test procedure based on a modified Bonferroni test. *Biometrika* 1988; 75, 383-386.

Spertus, J, et al. "Development and validation of the Atrial Fibrillation Effect on Quality-of-Life (AFEQT) Questionnaire in patients with atrial fibrillation." *Circ Arrhythm Electrophysiol*, Feb 4, 2011: 15-25.

STOP Persistent AF Statistical Analysis Plan

08-JUL-2019

Version 4.0

Page 25 of 25

Medtronic

U.S. Food and Drug Administration. "FDA Report: Collection, Analysis and Availability of Demographic Subgroup Data for FDA-Approved Medical Products." FDA Web Site.

<https://www.fda.gov/downloads/RegulatoryInformation/LawsEnforcedbyFDA/SignificantAmendmentstotheFDCA/FDASIA/UCM365544.pdf>. Published August 2013. Accessed April 28, 2017.

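### Does the SAP leave open whether Japanese subjects count in the FDA (PMA-S) tests?

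*SAP*

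**What the plan says.** The protocol gives the same answer in several places. The Synopsis, under study design, says: "Study data from the Japanese centers will not be included in the PMA-S submission, but will be included in a submission to Japan". The Synopsis row on sample size and timing, and section 17.2.1, say: "Study data from the Japanese centers will not be included in the PMA-S submission but will be made available". Section 7.1 repeats the exclusion, and section 17.1 defines the PMA-S cohort by region without Japan. The Synopsis gives the reason for separating Japan: enrolment there was expected to start later.

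SAP version 4.0, section 6.1.3, first says that the PMA-S will include subjects from US and Canadian centers. It then adds that, provided Japanese follow-up to 12 months is complete when the file goes in, "the Japan data may be included in the PMA-S submission". That same paragraph ends by setting the subjects used for the PMA-S (150 expected) apart from the PMDA cohort (165 expected).

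SAP section 6.3 names the subjects treated in the US and Canada as the PMA-S cohort and adds: "Heterogeneity analysis findings will not change the composition of the PMA-S and PMDA cohorts as defined above". The sample-size tables in sections 7.1 and 7.2 have separate rows for PMA-S (135 analysed) and PMDA (148 analysed). Section 7.2 states that "150 subjects in the US and Canada will provide 86% power" for safety.

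**The concern.** One document rules Japanese data out of the FDA submission and the other lets them in, and both are current text. No sentence says whether Japanese data, once included, would be pooled into the tests, shown separately or treated as supportive. The permissive sentence sits under the heading on analysis sets, where a reader looks to learn who is tested.

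The trial is single-arm and unblinded, the sponsor's statisticians analyse it, and each primary objective is decided by a confidence bound against a fixed goal. If the word 'may' left the test population to be chosen at submission, the sponsor could in principle see two results and use the one that passes. At stake would be the type I error of the two primary tests and the clarity of which population supports the FDA claim.

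**Working it through.** **1. Inputs.** Treated subjects: 150 (PMA-S) and 165 (PMDA), from protocol 17.1. After 10% attrition: 135 and 148, from SAP 7.1. Efficacy goal 40% with a planned rate of 54%; safety goal 13% with a planned rate of 5%; one-sided 0.025 for each. My assumptions are equal rates in all regions, nested cohorts (the larger is the smaller plus 15 or 13 Japanese subjects) and no partial follow-up, so that the Kaplan-Meier estimate is a simple proportion.

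**2. The plan's own figures.** With X binomial:

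| Test | Rule | Level at the goal | Power at the planned rate |
|---|---|---|---|
| Efficacy, 135 | X ≥ 66 | 0.0224 | 0.899 |
| Efficacy, 148 | X ≥ 72 | 0.0202 | 0.917 |
| Safety, 135 | X ≤ 9 | 0.0141 | 0.860 |
| Safety, 148 | X ≤ 11 | 0.0233 | 0.932 |

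All match SAP 7.1 and 7.2.

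**3. The planned log-log interval.** For success proportion S, the lower bound is S^exp(1.96·se), with se = √[(1−S)/(nS)] / |ln S|. The efficacy cutoffs for passing are 66/135, 72/148, 73/150 and 79/165. The safety cutoffs are 9/135, 10/148, 11/150 and 12/165. The efficacy levels with all treated subjects are:

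- P(X ≥ 73 | 150, 0.40) = 0.0193
- P(X ≥ 79 | 165, 0.40) = 0.0242

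Both are below 0.025.

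**4. If Japan were pooled on availability alone.** Suppose, against the likelier reading, that Japanese subjects entered the test whenever their data were complete, and that completeness is unrelated to results. The error is then w × 0.0242 + (1 − w) × 0.0193, where w is the chance that the data are ready. It lies between 1.9% and 2.4% for any w. On 135/148 it lies between 2.0% and 2.2%.

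**5. If the better cohort always counted.** The error is P(smaller passes) + P(smaller fails, larger passes):

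- Efficacy, 150/165: 0.01927 + 0.00885 = 0.0281.
- Efficacy, 135/148: 0.02240 + 0.00487 = 0.0273.
- Safety, 150/165: 0.02026 + 0.00224 = 0.0225.
- Safety, 135/148: 0.01409 + 0.00245 = 0.0165 with log-log cutoffs; 0.01409 + 0.01135 = 0.0254 with exact cutoffs.

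The largest excess over 0.025 is 0.3 of a percentage point.

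**6. How often the two cohorts disagree.** At the planned 54%, the efficacy verdicts differ with probability 0.0369 + 0.0039 = 0.041 for 150/165 and 0.0296 + 0.0115 = 0.041 for 135/148. The first term in each sum is a pass gained by adding Japan and the second a pass lost. Both cohorts are analysed by the same methods in any case, so this disagreement would exist without the sentence in SAP 6.1.3.

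**7. The texts side by side.** SAP 6.1.3 speaks of what a submission contains; SAP 6.3 names a cohort. Taken together they are consistent: the tests use the US and Canadian cohort, and Japanese results may accompany them in the file. The availability condition fits the protocol's timing reason for the separation. The protocol's remark that the Japanese data will be made available narrows the practical gap further.

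**The case for a change.** The best argument for a change is that the SAP blurs its own line. Section 6.3 defines the PMA-S cohort through what the submission includes, so altering the submission arguably touches the cohort. Section 6.1.3 also says that the SAP will not distinguish the two cohorts except where sample size matters. The protection in section 6.3 covers heterogeneity findings and is silent on data availability. Neither the visible version history nor section 6.8 lists the sentence as a departure from the protocol. A boundary case can be built: 72/150 fails (lower bound 39.8%) while 79/165 passes (40.1%). At a true success rate of 48%, assumed here because it is near the worst case, the verdicts differ with probability 11.4% (150/165) or 9.4% (135/148). One clarifying sentence would cost no patients and no power.

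What stands is the mismatch on submission content, and that the reading in which Japan is supportive only is inferred and not written. What does not stand is the step to an open test population. Section 6.1.3 still counts 150 for the PMA-S after the permissive sentence, and sections 6.3, 7.1 and 7.2 agree with it. Silence on availability in a sentence about heterogeneity does not license redefining a cohort. The boundary case and the 48% figure describe two planned analyses that can disagree anyway; they do not measure harm from this sentence.

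**Conclusion.** No change to the plan follows. The protocol and SAP 6.1.3 differ on what the FDA submission may contain, but the SAP defines, counts and powers the PMA-S cohort as about 150 US and Canadian subjects. An analyst following it would test that cohort and show any Japanese data beside it. No stated figure is wrong: the efficacy powers of 0.899 and 0.917 and the safety powers of 0.860 and 0.932 all reproduce.

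Used alone, each cohort's efficacy test holds its level (1.9% to 2.4%), and pooling on availability alone would stay in that range. Only choosing the better result after seeing both would exceed 2.5%, by at most 0.3 of a point for efficacy and by almost nothing for safety. The plan contains no such rule. These sizes rest on equal rates across regions, nested cohorts and no partial follow-up. The conclusion on the test population rests on reading SAP 6.1.3 together with 6.3 and 7. Wording added here would restate what those sections already imply and would not alter a sound result.
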